1. Compare total plaque volumes per-patient and per lesion as well as comparing different plaque type volumes to the IVUS reference standard and assess reproducibility of quantitative plaque measurements compared to the reference standard.
2. Perform exploratory analyses on plaque in previously stented vessels (protocol to allow up to 20% (50 patients) with one or two stented vessels in this category). This can also include

REVEALPLAQUE Study Protocol Version 1.0 August 12th, 2021

plaque proximal or distal to the stented vessel.

III. STUDY ENDPOINTS

III. A. Primary Endpoint

The primary endpoint is to assess the level of agreement between total plaque volume of a deep-learning based automated method for segmenting coronary atherosclerotic plaques, compared to IVUS, on a per-IVUS-pullback level.

III. B. Secondary Endpoints

Key secondary endpoints are:

Per pullback:

- Total plaque volume
- Percent plaque burden
- Calcified plaque volume
- Low attenuation plaque volume
- Fibrous plaque volume
- Segment involvement score (SIS)
- Adverse plaque characteristics (APC)

Per lesion:

- Total plaque volume
- Percent Plaque burden
- Calcified plaque volume
- Low attenuation plaque volume
- Fibrous plaque volume
- Minimum lumen area (MLA)
- Percentage area stenosis (%AS)
- Positive remodeling index

Per lesion/pullback:

- Reproducibility of all metrics above when quantified from different CCTA series
- Reproducibility of all metrics above when processing the same series twice (analyst and process variation)
- Exploratory analysis of necrotic core volume

IV. STUDY DESIGN

The REVEALPLAQUE study is a prospective, multi-center study designed to evaluate a deep-learning based automated method for segmenting coronary atherosclerotic plaques. All patients who have a stenosis confirmed by CCTA and FFR_{CT} available and who are scheduled to undergo IVUS will be eligible for enrollment. Enrolling sites will have FFR_{CT} analysis incorporated when indicated into their standard evaluation of CCTA scans. All sites will provide CCTA and FFR_{CT} images, full angiographic images, IVUS images, and if obtained, any other imaging or physiologic data including OCT, FFR, any NHPR (e.g., dPR, RFR, iFR, etc.), and pre- and post-stent implantation invasive data. All non-invasive and invasive data collected will be obtained as clinical practice consistent with standard clinical care.

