All details about cardiovascular testing and treatment (planned and actual) will be recorded at baseline.

REVEALPLAQUE Study Protocol Version 1.0 August 12th, 2021**IV. A. Location and Number of Subjects**

Approximately 250 subjects will be enrolled from approximately 15 experienced clinical research sites in the US and Japan.

IV. B. Patient Population

Clinically stable patients with known CAD who have a CCTA showing stenosis in at least one major epicardial vessel of stentable/graftable diameter and FFR_{CT} available, and in whom clinically indicated IVUS is planned within 45 days of CCTA will be prospectively enrolled.

IV. C. General Inclusion and Exclusion Criteria

Inclusion Criteria (all must be present):

1. Age \geq 18 years
2. Clinically stable patient with known CAD
3. CCTA showing stenosis in at least one major epicardial vessel of stentable/graftable diameter, in whom clinically indicated IVUS is planned within 45 days of the CCTA
4. CCTA meets eligibility criteria for FFR_{CT} as defined in the IFU
5. Willing to comply with all aspects of the protocol, including adherence to follow up visits
6. Agrees to be included in the study and able to provide written informed consent

Exclusion Criteria (all must be absent):

1. CCTA showing no stenosis
2. Uninterpretable CCTA by HeartFlow assessment, in which image quality prevents FFR_{CT} from being processed.
3. Acute chest pain
4. CABG prior to CCTA acquisition
5. Prior history of PCI for 3 or more vessels
6. MI less than 30 days prior to CCTA or between CCTA and ICA.
7. Suspicion of acute coronary syndrome (acute myocardial infarction or unstable angina)
8. Known complex congenital heart disease
9. Tachycardia or significant arrhythmia
10. Subject requires an emergent procedure
11. Evidence of ongoing or active clinical instability, including acute chest pain (sudden onset), cardiogenic shock, unstable blood pressure with systolic blood pressure <90 mmHg, and severe congestive heart failure (NYHA III or IV) or acute pulmonary edema
12. Any active, serious, life-threatening disease with a life expectancy of less than 2 months
13. Currently enrolled in another study utilizing FFR_{CT} or in an investigational trial that involves a non-approved cardiac drug or device
14. Persons under the protection of justice, guardianship, or curatorship

V. STUDY WORKFLOW

The workflow for the REVEALPLAQUE study is described in the following sections.

V. A. Study/Site Selection

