The REVEALPLAQUE study is a prospective study which collects data from clinically indicated CCTA imaging and ICA procedures. These procedures will have been planned as part of routine clinical practice; therefore, no additional clinical risks are related to participating in the study. Procedural complications will be documented that are related to IVUS or FFR (e.g., dissection from catheter or wire, reaction to medication).

IX. STATISTICAL CONSIDERATIONS**IX. A. General Considerations**

Descriptive statistical methods will be used to summarize the data from this study, with confidence intervals and hypothesis testing performed for the primary and other selected efficacy endpoints. Unless stated otherwise, the term “descriptive statistics” refers to number of events (n), mean, median, standard deviation (SD), standard error, minimum, maximum, and coefficient of variation (CV) for continuous data and frequencies and percentages for categorical data.

All data collected during the study will be included in data listings.

Unless specified otherwise, all statistical testing will be two-sided and will be performed using an overall significance (alpha) level of 0.05.

All statistical analyses will be conducted with the SAS® System, version 9.1.3 or higher.

A statistical analysis plan (SAP) will describe the methods of data collection, validation, analysis, and reporting. The sections below provide a brief overview of statistical consideration for the study.

IX. B. Subject Characteristics

Subject accountability will be described, including number of subjects enrolled, number of subjects included in the analysis, and reasons for any subjects discontinued from the study or not included in the analysis. Demographic information will be summarized using descriptive statistics. Sex and medical histories will be summarized by counts and percentages.

IX. C. Endpoint Analysis

The primary endpoint is to assess the level of agreement between total plaque volume of a deep-learning based automated method for segmenting coronary atherosclerotic plaques, compared to IVUS, on a per-IVUS-pullback level.

Bland Altman plots will be constructed. If the deep-learning based automated method CCTA measurements fall with the limits of agreement (LoA) estimated from the IVUS measurements, the

REVEALPLAQUE Study Protocol Version 1.0 August 12th, 2021

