measures will be assumed to agree. Additionally, Pearson's correlation and paired t-test will be constructed to further describe the relationship between IVUS measurements and deep-learning based automated method for segmenting coronary atherosclerotic plaques from CCTA.

All secondary endpoints which are continuous (e.g., per lesion total plaque volume, per lesion calcium volume, per lesion low attenuation volume, per lesion non-calcified plaque volume, segment involvement score) will be similarly compared using a Bland Altman plot, Pearson's correlation and paired t-tests. Reproducibility will be estimated with Intra Class correlation (ICC).

IX. D. Sample Size

Approximately 250 subjects may be enrolled into this study.

From published data (Conte 2019), the maximum allowable difference between the measurements is 36 mm³. Assuming a standard deviation of 12 mm³, a sample size of 223 patients achieves 90% power to detect agreement when the mean is 8, confidence level of the (LoA) is 0.950 and the confidence level of the confidence intervals about the LoA is 0.950.

IX. E. Analysis Populations

All subjects who meet the study criteria, sign the written informed consent, and are enrolled in the study, and provide paired assessments of CCTA and IVUS measurements will be included in the analysis set.

X. DATA HANDLING AND QUALITY ASSURANCE

X. A. Completing and Signing Case Report Forms

This study will utilize eCRFs for the collection of all data. Data changes and corrections for any errors should be corrected within the eCRF. The audit trail will record all changes made, the date and time of the correction, the person making the change, and a reason for the change. The appropriate electronic signature will be provided by the investigator as indicated.

X. B. Clinical Data Management

The sponsor or designee will be responsible for the processing and quality control of the data. The handling of data, including data quality control, will comply with all applicable regulatory guidelines.

The training of clinical site personnel in eCRF completion will be the responsibility of the sponsor or designee. To ensure uniform data collection, Case Report Form Guidelines will be created to assist with eCRF completion. All site staff including investigators and research coordinators will undergo site initiation training to become thoroughly familiar with the protocol, case report forms, and with methods of data verification.

X. C. Archiving of Data

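### IX.C names no patient-level method for its per-lesion comparisons (or for pullbacks, if a patient gives more than one), so confidence intervals may be too narrow and paired t-tests may reject too often

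*Combined protocol and SAP*

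**What the plan says.** **Unit of analysis.** The primary endpoint is total plaque volume "compared to IVUS, on a per-IVUS-pullback level" (III.A, IX.C). III.B lists seven secondary metrics per pullback and eight per lesion.

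**Methods.** For the primary endpoint, IX.C names Bland-Altman plots with LoA, and a Pearson correlation and "paired t-test will be constructed to further describe the relationship between IVUS measurements" and the CCTA method. The continuous secondary endpoints "will be similarly compared using a Bland Altman plot", Pearson correlation and paired t-tests. An intraclass correlation is named only for reproducibility.

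**Inference.** IX.A promises "confidence intervals and hypothesis testing performed for the primary and other selected efficacy endpoints", two-sided at 0.05. IX.D is built on intervals around the limits: "the confidence level of the confidence intervals about the LoA is 0.950".

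**Observations per patient.** IX.E defines the analysis set by subject: those who "provide paired assessments of CCTA and IVUS measurements will be included in the analysis set". Inclusion criterion 3 asks for "CCTA showing stenosis in at least one major epicardial vessel of stentable/graftable diameter", with no upper limit. V.D (ICA procedure, item 6) collects IVUS of non-target lesions where that is standard care. Secondary objective 1 is to "Compare total plaque volumes per-patient and per lesion as well as comparing different plaque type volumes to the IVUS reference standard", so patient and lesion are distinct units.

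**Deferral.** IX.A calls Section IX a brief overview and leaves the analysis methods to a SAP.

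**The concern.** Two lesions in one patient would usually share the CCTA scan, the IVUS procedure and the patient's anatomy and image quality. Their CCTA-minus-IVUS differences are therefore likely to be positively correlated. A second lesion from the same patient then carries less information than a lesion from a new patient, but the ordinary formulas count both in full.

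At stake is the stated precision. Intervals for the bias and the LoA would make agreement look better established than it is. For a secondary endpoint with bias near zero, the paired t-test would report a difference more often than 5% of the time.

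**Working it through.** **1. The plan's own figure.** IX.D gives a maximum allowable difference of 36 mm³, mean 8, SD 12, 95% LoA, 95% intervals about the LoA, 223 patients and 90% power.

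- Upper LoA = 8 + 1.96 × 12 = 31.52 mm³.
- SE of a limit = 12 × √(1/223 + 1.96²/(2 × 222)) = 1.375 mm³.
- Distance to 36 in SE units = (36 − 31.52)/1.375 = 3.26.
- With a two-sided 95% interval and the non-central t distribution on 222 df, power is 0.900.

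So 223 reproduces, with one independent difference per patient.

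**2. Effect of clustering.** Let patient i give mᵢ observations, let rho be the correlation of differences within a patient (compound-symmetric normal model), and let k = Σmᵢ(mᵢ − 1)/Σmᵢ. The correct SE exceeds the ordinary SE by these factors:

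- bias: √(1 + rho·k)
- LoA: √{[1 + rho·k + (1.96²/2)(1 + rho²·k)] / (1 + 1.96²/2)}

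For 223 patients, k = 88/267 = 0.33 if 44 patients (20%) give a second observation, k = 1 if all give two and k = 2 if all give three. Example with all giving two and rho = 0.5:

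- bias: √1.5 = 1.22
- LoA: √[(1.5 + 1.92 × 1.25)/2.92] = 1.16

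**3. Coverage of ordinary 95% intervals.** These come from simulation (40,000 trials per setting, mean 8, SD 12), and coverage computed from the formulas agrees within 0.3 points. The values of m and rho are assumptions.

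| Setting | rho | SE factor, bias | SE factor, LoA | Coverage, bias | Coverage, upper LoA |
|---|---|---|---|---|---|
| One each | any | 1.00 | 1.00 | 95% | 95% |
| 20% give a second | 0.1 / 0.3 / 0.5 | 1.02 / 1.05 / 1.08 | 1.01 / 1.03 / 1.05 | 94.6 / 93.7 / 93.2% | 94.8 / 94.4 / 93.7% |
| All give two | 0.1 / 0.3 / 0.5 | 1.05 / 1.14 / 1.22 | 1.02 / 1.08 / 1.16 | 93.7 / 91.4 / 89.0% | 94.4 / 93.1 / 90.9% |
| All give three | 0.1 / 0.3 / 0.5 | 1.10 / 1.26 / 1.41 | 1.04 / 1.15 / 1.29 | 92.5 / 87.8 / 83.5% | 93.8 / 91.4 / 87.1% |

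Three per patient is plausible only for lesions.

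**4. Paired t-test.** At zero bias it rejects exactly when the bias interval excludes zero, so its error rate is 100% minus the bias coverage:

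- 20% give a second: 5.4 / 6.3 / 6.8%
- all give two: 6.3 / 8.6 / 11.0%
- all give three: 7.5 / 12.2 / 16.5%

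**5. What does not move.**

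- The mean estimated SD stays at 11.98–11.99 against a true 12, so the point LoA hardly change.
- With IX.D's values the primary t statistic is 8/(12/√223) = 9.96 with one pullback each. With 20% giving a second and rho = 0.5 it is 8/(12/√267) = 10.89 uncorrected and 10.89/1.079 = 10.1 corrected.
- IX.D counts patients, so extra pullbacks add information. With 20% giving a second, power is 94.4 / 93.6 / 92.3% at rho 0.1 / 0.3 / 0.5, against 90% with one each.

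**6. Remedies.** Across the clustered settings, patient-clustered SEs cover 94.7–95.3% (bias) and 94.3–94.9% (upper LoA). A percentile bootstrap of patients covers 94.3–94.9% and 93.7–94.3%. For the LoA at 20% and rho = 0.1, neither improves on the ordinary 94.8%. The gain comes with stronger clustering.

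**The case against.** **The methods are deferred to a SAP.** This is true, and that SAP may supply a patient-level method. A reader might infer that the sponsor has chosen to assume independence. The documents do not show that: IX.C states no interval formula at all. What stands is that the text names specific methods and omits this one. Adding it to the SAP would settle the point.

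**The primary endpoint may have one pullback per patient.** This is a fair objection, and it limits the point. IX.D counts patients and reproduces with one difference each. VI.B refers to a single vessel. Inclusion criterion 3 concerns stenosed vessels on CCTA, not pullbacks, and a non-target lesion may lie on the same pullback as the target. Objective 1 is also compatible with one pullback per patient. Several lesions per patient is much the better supported case.

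**No stated conclusion changes.** For the primary endpoint this is largely right: the agreement rule in IX.C uses no confidence interval, and the t-test is descriptive. IX.A does not say which secondary endpoints will have intervals, and no secondary bias is given, so a secondary endpoint with bias near zero is a supposition.

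**The sample size.** A reader might infer that 223 is too small. It is not shown to be. That would follow only if 223 meant pullbacks, and IX.D says patients.

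**The size is assumed.** This is correct. The largest losses need every patient to give three observations, which nothing in the documents establishes. The effect on Pearson's correlation was not quantified, because it also depends on how plaque volumes themselves correlate within a patient.

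**Conclusion.** The point holds for the per-lesion secondary endpoints, and for per-pullback endpoints only if some patients give more than one pullback. The omission can be read directly from the text, and the direction of the error is certain if within-patient differences are positively correlated. Its size is not known. Over the assumed range, the loss of bias coverage runs from under half a percentage point (20% give a second, correlation 0.1) to about 11.5 points (three lesions each, correlation 0.5), with smaller losses for the LoA. With one observation per patient, or zero correlation, there is no error.

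This is a point about reported precision and secondary p-values. It does not call the primary conclusion or the enrolment target into question. It should be corrected because the remedy is cheap.

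**What to change.** Add to IX.C or the SAP:

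- Confidence intervals for the mean difference and for each LoA use patient-clustered standard errors; the limits themselves still use the SD of all differences. For the LoA, a linearised form works: for each difference d, take (d − mean) ± 1.96[(d − mean)² − s²]/(2s), sum within patient, and base the variance on the patient sums.
- The paired t-test is replaced by a test of the mean difference with patient-clustered standard errors.
- Any interval or p-value for Pearson's correlation is clustered by patient.
- The numbers of lesions and pullbacks per patient are tabulated.

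For the primary endpoint, one pullback per patient, chosen by a rule fixed before data are seen, is an acceptable alternative. Clustered standard errors are preferable to a percentile bootstrap for the LoA.

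**Cost.** A few lines of text and modest programming, with no new data and no change to IX.D. At correlations of 0.1 to 0.5, the bias interval widens by about 2–8% if 20% of patients give a second observation, 5–22% if all give two and 10–41% if all give three. The LoA interval widens by about 1–5%, 2–16% and 4–29%. If every patient gives one observation, almost nothing changes.

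### Lesions with no calcified or no low attenuation plaque may enter the pooled agreement analysis as zero-zero pairs, which dilutes the bias and usually narrows the limits for lesions that contain the component

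*Combined protocol and SAP*

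**What the plan says.** Section III.B lists component volumes, among them "Low attenuation plaque volume", as key secondary endpoints both per pullback and per lesion. Section IX.C gives all continuous secondary endpoints one method. Its examples include "per lesion calcium volume, per lesion low attenuation volume, per lesion non-calcified plaque volume, segment involvement score", and these "will be similarly compared using a Bland Altman plot, Pearson's correlation and paired t-tests". The word 'similarly' points back to the primary rule, which begins "If the deep-learning based automated method CCTA measurements fall with the limits of agreement (LoA) estimated from the IVUS measurements" and then takes the two measures to agree.

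Section IX.E defines the analysis set: enrolled, eligible subjects who "provide paired assessments of CCTA and IVUS measurements will be included in the analysis set". Nothing in the protocol counts zero volumes, assesses agreement on presence or absence, or restricts the limits to lesions that contain the component. Section IX.A says of the statistical sections: "The sections below provide a brief overview of statistical consideration for the study". It leaves the detail to an SAP, and the text available contains no further detail on this point.

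**The concern.** The primary endpoint is total plaque volume. A stenosis is required for entry, so a zero total should be rare. Nothing requires every lesion to contain calcified or low attenuation plaque, and the lesion is the small unit in which absence is most plausible. A method suited to total volume is therefore carried over to variables that may have a point mass at zero.

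A zero-zero pair shows that absence was correctly recognised. It does not show how well volume is measured where the component is present. Pooling answers both questions with one set of limits. The secondary hypothesis in the synopsis claims accurate assessment of calcified and low attenuation volumes, and section I singles out low attenuation plaque as important for identifying patients at risk of infarction. The reported bias, limits and correlation could look better because the component is absent from more lesions, not because it is measured better.

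**Working it through.** **Inputs.** From section IX.D: maximum allowable difference 36 mm³, mean difference 8 mm³, SD 12 mm³, 95% limits, 95% confidence intervals about them, 90% power, 223 patients. Mean and SD are planning values for total plaque volume and are borrowed here only as an illustration. The share p of pairs that are zero by both methods is not in the documents; the assumed range is 10% to 70%. 'Component-present' means that at least one method is above zero. Differences in those pairs are taken as normal with mean m and SD s.

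**1. The plan's own figure.** SE of a limit = SD·sqrt(1/n + 1.96²/(2(n-1))). At n = 223 this is 12 × 0.1146 = 1.375. The distance from the nearer limit to the margin is 36 - 8 - 1.96 × 12 = 4.48, so the non-centrality is 4.48/1.375 = 3.26. A non-central t calculation for both limits gives power 0.9004, and 223 is the smallest n that reaches 90%. The figure is reproduced and does not depend on zero volumes.

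**2. Effect of pooling.** With a share p of differences exactly zero:

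- pooled mean = (1-p)·m
- pooled SD = sqrt((1-p)(s² + p·m²))
- pooled SD < s exactly when |m| < s/sqrt(1-p)

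With s = 12 the condition is strictest at the smallest p: 12/sqrt(0.9) = 12.6, so m = 8 meets it throughout the range. For example, at p = 50% the pooled mean is 4, the pooled SD is sqrt(0.5 × (144 + 32)) = 9.38, and the limits are 4 ± 1.96 × 9.38 = -14.4 to 22.4. Coverage of component-present pairs is Phi((22.4 - 8)/12) - Phi((-14.4 - 8)/12) = 85.4%.

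| p | Pooled mean | Pooled SD | Pooled limits (mm³) | Width relative to component-present | Coverage of component-present |
|---|---|---|---|---|---|
| 0 | 8.0 | 12.00 | -15.5 to 31.5 | 1.00 | 95% |
| 10% | 7.2 | 11.63 | -15.6 to 30.0 | 0.97 | 94.2% |
| 30% | 5.6 | 10.69 | -15.3 to 26.5 | 0.89 | 91.3% |
| 50% | 4.0 | 9.38 | -14.4 to 22.4 | 0.78 | 85.4% |
| 70% | 2.4 | 7.53 | -12.4 to 17.2 | 0.63 | 73.2% |

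**3. Sensitivity to bias.** With m = 0 the width ratio is sqrt(1-p): 0.95, 0.84, 0.71 and 0.55 at the same four shares, with coverage 93.7%, 89.9%, 83.4% and 71.7%. With m = 24 the condition fails and pooling widens the limits: ratio 1.24 at p = 30% (coverage 96.5%) and 1.23 at p = 50% (coverage 91.9%). The dilution of the mean to (1-p)·m holds for any non-zero bias.

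**4. Pearson's r.** If both methods have the same mean and SD in component-present pairs, with coefficient of variation c and correlation r, the pooled correlation is (r·c² + p)/(c² + p). With r = 0.50 and c = 0.5 it is 0.425/0.55 = 0.77 at p = 30% and 0.625/0.75 = 0.83 at p = 50%. With c = 1.0 it is 0.8/1.3 = 0.62 and 1.0/1.5 = 0.67.

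**The case against.** The strongest reply is that pooled limits are a legitimate target. A zero-zero pair is a correct negative, and the all-pairs limits describe a lesion drawn from the sampled population. Under the planning values, the share of all lesions outside them is (1-p) times the share of component-present lesions outside: 0.7 × 8.7% = 6.1%, 0.5 × 14.6% = 7.3% and 0.3 × 26.8% = 8.0% at p = 30%, 50% and 70%. That stands. The pooled limits are not wrong in themselves, but they do not support a claim about volumetric accuracy where the component exists.

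A reader might infer that zero volumes are common. The documents give no frequency, no definition of a component and no threshold. Both methods must read exactly zero, and every patient has known disease with stenosis. The share could be small, and at 10% the limits narrow by only 3% (5% with no bias).

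A reader might also infer that pooling always narrows the limits. It does so only under the bias condition above.

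Finally, section IX calls itself an overview, so an SAP may settle the matter. This is an omission in the text available, not a proven fault of the final analysis. It does not remove the point, because IX.C already names the method for these endpoints.

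**Conclusion.** The point holds in conditional form and is worth correcting. IX.C pools all pairs for per-lesion calcified and low attenuation volumes and has no rule for pairs that are zero by both methods. If such pairs occur, any non-zero bias is diluted to (1-p) of its value. At the protocol's ratio of mean to SD (8/12), the limits also undercover lesions that contain the component: slightly at p = 10%, materially from about 30% upward.

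The size rests on an assumed p, on total-plaque planning values borrowed for components, and on normal differences within component-present pairs.

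A reader might extend this to the primary result or to the 223 patients. The documents do not support that: the primary endpoint is total plaque volume, and the sample size calculation does not involve component volumes. Nor is a pass/fail decision shown to change, because no numeric margin is set for any component; the 36 mm³ appears only in section IX.D. The consequence is confined to how bias, limits and correlation are reported for these secondary endpoints.

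**What to change.** In section IX.C or the SAP, before results are seen, specify for per-lesion calcified and low attenuation volumes:

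1. The number of pairs that are zero by both methods, by one and by neither, with a 2×2 table of presence or absence by CCTA against IVUS.
2. Bias, limits of agreement and Pearson's r in pairs where at least one method is above zero, as the result that supports the volumetric accuracy claim. Report the all-pairs limits beside them, labelled as describing all sampled lesions.

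Apply the same to per-pullback volumes only if zero-zero pairs occur there.

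The cost is some wording and a few tables; no new data are needed. The restricted analysis has fewer pairs, so its limits are less precise and will usually look wider. For example, if 223 independent pairs fell to 112, the 95% confidence half-width of each limit at SD 12 would rise from 1.96 × 1.375 = 2.7 to about 3.8 mm³. If zero-zero pairs prove rare, the two sets of results will nearly coincide.
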